8. ANALYTICAL PLAN AND STATISTICAL METHODS

8.1 GENERAL CONVENTIONS AND STATISTICAL CONSIDERATIONS

All statistical analyses will be performed and data appendices will be created using the SAS system version 9.4 or higher.

Summary statistics for continuous variables will include number of patients with nonmissing values, number of patients with missing values, mean, standard deviation, median, Q1 (quartile 1), Q3 (quartile 3), minimum and maximum values.

Summary tables for categorical variables will include number and percentage of patients for each category. If not specified additionally, number of patients with non-missing values will be the denominator for percentage calculation. The number of patients with missing values will be presented.

All the analyses will be run displaying by treatment arm and overall.

Unless otherwise stated, all statistical tests will be performed using two-sided tests at the 5% significance level.

If necessary, the statistical analytical plan and statistical methods section may be updated before the database lock. Any changes in statistical methods that may have an impact on the primary conclusions drawn from this clinical trial will be described in an amendment to the protocol. All other changes in the statistical plan will be described in section 9.8 of the clinical study report (CSR). An explanation will be provided for deviations from the planned analysis.

After the last subject completes the end of the short term follow-up phase the database will be locked and the study will be unblinded for the purpose of the statistical analysis. Evaluation of all efficacy and safety endpoints will occur. Evaluation of PK and PD endpoints will occur at a later stage, as well as the genomic analyses. Note: the PD and genomic analyses will only be performed if the study has a positive efficacy outcome. The overall tumor response to chemoradiation therapy will be evaluated following the second database lock after the last subject completes the long term follow-up phase (i.e. 12 months after the last dose of CRT).

A full study report will be written after completion of the statistical analysis including the evaluation of the efficacy and safety endpoints as described in Section 10.1. The PK data and overall tumor response to chemoradiation therapy will be described in an addendum to the study report, as well as PD endpoints and genomic analyses (in case of positive primary endpoint) after (a) later database lock(s).

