8.7 EFFICACY ENDPOINTS AND ANALYSIS

8.7.1 ANALYSIS OF PRIMARY EFFICACY ENDPOINT

The duration of severe OM (WHO grade 3 or 4) will be calculated as the number of days from the onset of severe OM (first time a WHO grade 3 or 4 is observed) to the day when severe OM has resolved (first time WHO grade 2 or less is observed after last WHO grade 3 or 4). This calculation allows for fluctuation in severity grades and considers separate episodes of SOM to be additive. Durations of 0 will be assigned to subjects who do not experience severe OM, even if the subject was not followed for the full planned period. Any subject who dies or withdraws prior to resolution of severe OM (i.e., with grade 3 or 4 at last assessment) will be assumed to have severe OM for the remainder of the observation period. In these cases, duration will be calculated as the number of days from the first onset of severe OM (WHO grade 3 or 4) until the end of Short Term Follow-up phase which will be taken as Week 13 (Day 91 relative to start of CRT). All available OM assessments will be used to derive efficacy endpoints, including WHO grades recorded during the treatment phase and the short-term follow-up period.

The intent of the primary statistical analysis is to test the superiority of AG013 over placebo in reducing the duration of severe OM. The null hypothesis is that the AG013 and placebo groups have the same duration (in days) of severe OM. The alternative hypothesis is that the duration of severe OM in the two treatment groups is different.

The generalized CMH method, stratified by cisplatin regimen (weekly versus tri-weekly), by HPV status (positive versus negative) and region (US versus Europe), will be used for the primary efficacy analysis. In case of erroneous stratification at baseline, the corrected stratification data will be used for the analysis. Standardized mid-ranks (also known as modified ridit scores) will be used for the test statistic. This generalized CMH test follows a chi-square distribution with 1 degree of freedom. The efficacy analysis will be performed in the ITT, mITT, and PP populations, with the ITT designated as primary. Below is the sample code that performs this analysis:

```
proc freq
```

```
data=test;
tables STRATUM*TRTPN*OM_DURATION / CMH SCORE=MODRIDIT;
run;
```

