8.7.2 ANALYSIS OF KEY SECONDARY EFFICACY ENDPOINTS

Statistical methods for the calculation and analysis of secondary efficacy endpoints are provided below. For each endpoint, significance testing will evaluate the superiority of AG013 compared to placebo; two-sided tests will be used to reject the null hypothesis (no difference between groups) in favor of the alternative hypothesis (there is a difference between groups). The analysis of all key secondary efficacy endpoints will be performed for the ITT, mITT and PP populations.

Note: The OM assessment period includes all OM Assessments performed, including the short-term follow-up period.

To control the experiment-wise Type 1 error rate at 5%, significance tests of the key secondary efficacy endpoints will be performed in the hierarchical order listed below. As specified in the protocol, the mITT population will be the main analysis and guide the hierarchical order of testing. To support these results, the same analyses will be repeated for ITT and PP populations. Each analysis will control for stratifications factors. All the analyses described below will be performed for the purpose of displaying summary statistics, but once the first in the sequence of tests yields a p-value that exceeds 0.05, the nominal p-value for this and subsequent endpoints in the series will be declared non-significant.

Time to onset of severe OM: Time to onset of severe OM (WHO grade 3 or 4) will be calculated as the elapsed time (in days) from the start of CRT until the date of first OM assessment grade 3 or 4. Subjects who do not experience an event by the end of the OM assessment period will be censored on the date of last OM assessment. Subjects with no post-baseline OM assessments will be censored on Day 1. Kaplan-Meier estimation methods and the stratified log-rank test will be used to compare time-to-event distributions and test whether or not AG013 delays the onset of severe OM. The log-rank test will be stratified by cisplatin regimen, HPV status and region. Below is the sample SAS code that performs the intended analysis:

```
proc lifetest
```

```
data=test;
time Time_to_Onset*censor(1);
strata CIS_GRP HPV REGION / group=TRTPN;
run;
```

Incidence of severe OM: The incidence of severe OM (WHO grade 3 or 4) will be calculated as the number of subjects with at least one OM WHO grade 3 or 4, divided by

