the number subjects in the treatment group. A stratified CMH test (general association statistic) will be used to compare proportions and test whether or not AG013 reduces the incidence of severe OM. Incidence will be calculated for two observation periods: (1) entire follow-up period, and (2) from the first to last day of CRT. Incidence of severe OM will also be summarized descriptively for subgroups defined by 3 factors (cisplatin regimen, region, HPV status) in the mITT population only.

Duration of ulcerative OM: The duration of ulcerative OM (WHO grade 2, 3 or 4) will be calculated in a manner similar to duration of severe OM. That is, the duration of ulcerative OM will be calculated as the number of days from the onset of ulcerative OM (first time a WHO grade 2, 3 or 4 is observed) to the day when ulcerative OM has resolved (first time WHO grade 0 or 1 is observed after last WHO grade 2, 3 or 4). An imputation scheme similar to the primary analysis will be used in the event that subjects discontinue prior to resolution of OM to grade 0 or 1. The stratified CMH test (with modified ridit scores) will be used to compare treatment groups and test whether or not AG013 reduces the duration of ulcerative OM.

Time to onset of ulcerative OM: Time to onset of ulcerative OM (WHO grade 2, 3 or 4) will be calculated and analyzed as described above for severe OM.

Incidence of ulcerative OM: Incidence of ulcerative OM (WHO grade 2, 3 or 4) will be calculated and analyzed as described above for severe OM.

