^h AEs and SAEs with onset after the subject signed the ICF through the end of short term follow-up will be recorded on the CRF. All subjects with AEs or SAEs will be followed until the events resolve, stabilize, become chronic, the subject completes the study, or the subject is lost to follow-up.

ⁱ The OMDQ must be completed daily. On visit days the OMDQ must always be completed prior to the OM assessment. (see sections 7.3.1, 7.3.2, 7.3.4, and 7.3.5)

^j Subjects with WHO persistent grade mucositis of 2 or greater at the end of the active treatment phase will continue to complete the daily diaries in the short term follow-up period until mucositis decreases to grade of 0 or 1. If OM has not decreased to less than grade 2, weekly OM assessments will continue until OM is a grade 1 or less.

^k The first dose of IMP should be witnessed by a study staff member. IMP dosing will continue three times per day until Day 14 Post CRT visit.

¹Planned continuous course of intensity-modulated radiotherapy (IMRT) with a minimum cumulative dose of 50 Gy and maximum dose of 72 Gy.

^mAssessments to be carried out on weekly base during the active treatment phase, during one of both twice-weekly visits

ⁿ Clinical laboratory measurements (15 ml blood to be taken per sampling) will include CBC (WBC cell count differential in %, hemoglobin, hematocrit, platelet count, RBC indices) and chemistry profile (sodium, glucose, potassium, BUN, creatinine, phosphorus, calcium, alkaline phosphatase, LDH, AST, ALT, and albumin).

^o Samples for biomarker studies, genetic samples or PK sampling, taken during active treatment period should be drawn at the last RT day of a specific week (see section 7.3.3.).

^p Draw blood samples for biomarkers studies (10 ml blood to be taken per sampling) at baseline, week 3 and 5, on the last day of RT, on the last day of IMP and 4 weeks after the end of RT (equals week 2 of the short term follow-up).

^q If a subject consents separately, draw blood samples (2,5 ml blood to be taken per sampling) for genetic responder/non-responder studies (baseline visit and on the last day of RT).

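### Day 91 ends the mucositis duration only for subjects who die or withdraw unresolved; observed durations have no stated limit, so the two kinds are ranked on different windows

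*SAP*

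**What the plan says.** SAP 8.7.1 has two end rules for severe OM.

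- **Observed durations** end the "first time WHO grade 2 or less is observed after last WHO grade 3 or 4". The same paragraph adds: "All available OM assessments will be used to derive efficacy endpoints". No upper limit is given.
- **Imputed durations** are for this group: "Any subject who dies or withdraws prior to resolution of severe OM (i.e., with grade 3 or 4 at last assessment"). They run from first onset "until the end of Short Term Follow-up phase which will be taken as Week 13 (Day 91 relative to start of CRT").

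Both kinds are then ranked together with modified ridit scores in the stratified CMH test.

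SAP 8.7.2 carries this over to the duration of ulcerative OM: "An imputation scheme similar to the primary analysis will be used in the event that subjects discontinue prior to resolution of OM". Resolution there means grade 0 or 1. The section also notes: "The OM assessment period includes all OM Assessments performed, including the short-term follow-up period".

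The documents disagree on when grading stops. SAP Appendix I, footnote j, says: "If OM has not decreased to less than grade 2, weekly OM assessments will continue until OM is a grade 1 or less". Protocol 6.3.1, 7.3.5 and Appendix D agree with that. Protocol section 3 and SAP 4.1 instead stop grading at the end of short-term follow-up or at resolution, whichever is earlier.

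On the first lock, SAP 8.1 says: "After the last subject completes the end of the short term follow-up phase the database will be locked".

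**The concern.** In a rank test the order of the durations is the result. Here the order depends partly on why follow-up ended. A subject who leaves unresolved (a leaver) stops accruing days on Day 91. A subject who stays keeps accruing until healing is seen. Three problems follow.

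1. At equal onset, anyone who heals after Day 91 ranks worse than a leaver who was never seen to heal.
2. A leaver whose last severe grade falls after Day 91 is given an end date earlier than that observation.
3. A completer still unresolved when grading stops or the database locks has not resolved, died or withdrawn, so neither end rule applies.

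At stake are the primary endpoint and key secondary 3. The second is the more exposed, because extended grading is triggered by grade 2 or more.

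**Working it through.** **Reproducing Day 91.** The longest active phase is 9 weeks and short-term follow-up is 4 weeks (SAP 4.1, Table 1): 13 x 7 = 91. Equivalently, last CRT on Day 49 plus 42 days = Day 91. The figure is right for a 7-week course.

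**Can grades fall after Day 91?** Inputs: 2.0 to 2.2 Gy daily and 50 to 72 Gy in total (Protocol 4.2), and the last visit at Day 42 post-CRT, plus or minus 3 days. I assumed five fractions a week, no interruption and any weekday start. End of follow-up = last RT day + 42.

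| Course | Last RT day | End of follow-up | With window |
|---|---|---|---|
| 50 Gy / 2.0 = 25 fractions | 33-35 | 75-77 | 72-80 |
| 70 Gy / 2.0 = 35 fractions | 47-49 | 89-91 | 86-94 |
| 72 Gy / 2.0 = 36 fractions | 50 | 92 | 89-95 |

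A 5-day break moves the last two to as late as 49 + 5 + 42 = Day 96 and 50 + 5 + 42 = Day 97. So grades can fall after Day 91 even if grading stops at the end of short-term follow-up. Under extended weekly grading they can fall well after it.

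**Scores under the rule.** Duration = end day minus onset day. Counting inclusively would add 1 to every non-zero value and change no comparison.

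| Subject | As written | One window to Day 91 |
|---|---|---|
| Severe, onset 30, leaves unresolved | 91 - 30 = 61 | 61 |
| Severe, onset 30, heals Day 105 | 105 - 30 = 75 | 61 |
| Severe, onset 30, grade 3 last seen Day 99, then withdraws | 61, although 99 - 30 = 69 were observed | 61 |
| Severe, onset 95, withdraws unresolved | 91 - 95 = -4 | 0 |
| Ulcerative, onset 18, dies Day 40 | 91 - 18 = 73 | 73 |
| Ulcerative, onset 18, heals Day 106 | 106 - 18 = 88 | 73 |

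**Size for severe OM.** The documents do not give the share still affected after Day 91, so this simulation rests on assumptions: 100 per arm, 70% incidence in both arms, onset uniform over Days 20-45, gamma durations with mean 15, 20 or 25 days, 5% to 15% leaving unresolved, an unstratified rank-sum test and 1500 runs. Between 0.7% and 4.9% of subjects heal after Day 91. In 63% to 79% of pairs of a leaver and a late healer, the leaver ranks better. The largest change in rejection rate between the rule as written and a common Day 91 window is 7.1% v 8.0%, or 0.9 points.

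**Size for ulcerative OM.** Assumptions: 100 per arm, no treatment effect, onset N(18, 5), resolution at Day 47 plus N(22, 14), N(28, 16) or N(32, 16), leaving time uniform over Days 22-60 while unresolved, leaving probability 25% v 10%, 2000 runs. Positive z means that the arm with more leavers is scored worse; with complete data mean z is about 0.

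| Completers resolving after Day 91 | 6% | 16% | 23% |
|---|---|---|---|
| Completer-leaver pairs in which the completer scores longer, as written | 8% | 18% | 24% |
| Same, one window | 6% | 13% | 17% |
| Mean z, as written | 1.33 | 1.04 | 0.85 |
| Mean z, one window | 1.38 | 1.21 | 1.10 |
| Two-sided 5% rejection, as written | 27% | 18% | 14% |
| Same, one window | 28% | 22% | 20% |

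With 15% v 10% leavers, the two rules differ by at most about 0.1 in mean z.

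**The case against.** The strongest objection is that the common window does not bring the test nearer to the truth in the ulcerative simulation. There is no treatment effect there, yet mean z and the false rejection rate both rise. That stands. The window applies the assumption that leavers stay unresolved consistently, and this assumption is what penalises the arm with more leavers. The case for the window is a coherent endpoint, not less dropout bias.

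Most completer-leaver pairs in which the completer scores longer also remain (6 of 8, 13 of 18 and 17 of 24 percentage points). They reflect earlier onset in the completer, which is legitimate. The window removes only the reversals caused by unequal end dates.

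It can be said that SAP 4.1 stops grading at the end of short-term follow-up, and that SAP 8.7.1 names only treatment-phase and short-term follow-up grades. That conflicts with footnote j, so the absence of a limit is not beyond dispute. But even on that reading grades can fall on Days 92-95 without any delay, and a completer still at grade 3 or 4 has no defined duration.

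SAP Table 1 mentions extended follow-up inside the short-term row, so the lock might be meant to wait for it. If so, the gap at lock closes, but Week 13 is then no longer the end of that phase.

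For severe OM, SAP 8.7.1 already lists two total-days sensitivity analyses that end at short-term follow-up for everyone, one with median imputation for unresolved OM, and one ending at last CRT. These largely protect the interpretation of the primary. None is listed for ulcerative duration.

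The SAP date is also later than the one in Protocol 10.5 (2 weeks after the last planned CRT dose), which lessens the reversal. For a 25-fraction course Day 91 lies 14 to 16 days beyond the subject's own scheduled end, so there the rule is harsher on leavers.

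**Conclusion.** The inconsistency stands and should be corrected before unblinding. As written, the rule can rank a leaver better than a same-onset subject who heals after Day 91, score a leaver below the days observed, and return a negative duration. It can also leave some completers without a value.

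The effect on the primary is probably small: under the assumed inputs, under 1 percentage point in rejection rate. For ulcerative duration it could be moderate, but that endpoint is tested only if the primary and two key secondaries succeed. Both sizes rest on persistence and leaving rates that the documents do not give.

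A reader might infer three stronger things that the documents do not support.

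- **That severe days after Day 91 are deleted in general.** Only subjects who die or withdraw with a last severe grade after Day 91 lose days; healers keep all of theirs.
- **That the arm with more leavers gains an advantage.** In the simulation it is still scored worse than under complete data, only by less than under a common window.
- **That the SAP promises leavers the worst rank and breaks the promise.** SAP 8.3 reserves worst-case assumptions for subjects with no OM assessments. For leavers, 8.7.1 assumes only that severe OM lasts through the remaining observation period.

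**What to change.** In SAP 8.7.1, and by reference for ulcerative OM in 8.7.2:

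- Use one observation window for observed and imputed durations: count from onset to the earlier of observed resolution and Day 91.
- Count to Day 91 every subject not seen to resolve by then, whether dead, withdrawn, in extended grading or unresolved at lock.
- Score onset after Day 91 as 0 in the tested duration.
- Report OM beyond Day 91 descriptively by arm.
- Add a sensitivity analysis, for both durations, that keeps late observed days and counts leavers to the later of Day 91 and their last unresolved assessment. It shows what the late data contribute; it does not remove the same-onset reversal.
- Reconcile Protocol section 3 and SAP 4.1 with Protocol 7.3.5 and SAP Appendix I on when OM grading stops, and state whether the lock waits for extended grading.
- List the end date in SAP section 9, which does not record the change from Protocol 10.5.

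The cost is a few sentences of SAP text, a minimum and a floor at zero in the derivation, one table and one extra analysis. No new data or subjects are needed. SAP 8.1 allows updates before lock, but requires a protocol amendment if the change may affect the primary conclusions.

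Two downsides should be stated in the SAP. Late days in the few persisters leave the tested duration. The penalty on the arm with more unresolved leavers also becomes slightly larger, as the simulation shows.

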8.3 HANDLING OF MISSING DATA

All available efficacy and safety data collected for the study will be included in data listings and/or summary tables. Every effort will be made to obtain required data at each scheduled evaluation from all subjects enrolled. Rules for deriving efficacy endpoints will utilize imputation rules as specified in the efficacy analysis section. Sensitivity analyses will be performed to ensure that results of the primary efficacy endpoint are robust and not explained by missing or incomplete data. Worst-case assumptions will be applied to subjects who do not have OM assessments during the study period. Where necessary, missing assessments of OM will be imputed using multiple imputation procedures. Select exploratory sensitivity analyses will be conducted to ascertain the effect, if any, of these methods. No other missing data will be imputed.

Any imputation of missing or incomplete data will be flagged in the analysis data sets. The original value will be kept for traceability.

Incomplete dates imputation.

The following rules will be applied for AEs and concomitant medications with incomplete dates:

- If Day is missing for Start Date and Month and Year are the same as Month and Year for the First Dose of IMP Date, then Start Date equals First Dose of IMP Date.
- If Day is missing for Start Date and Month and Year are not the same as Month and Year for the First Dose of IMP Date, then impute Day 1 of the Month.

- If Day and Month are missing for Start Date and the Year is the same as the Year for the First Dose of IMP Date, then Start Date equals First Dose of IMP Date.
- If Day and Month are missing for Start Date and the Year is less than Year for the First Treatment Date, then impute July 1st of the Year.
- If Day and Month are missing for Start Date and the Year is greater than Year for the First Treatment Date, then impute January 1st of the Year.
- If the entire Start Date is missing, set it equal to First Dose of IMP Date.

No imputation for the end date of AEs will be done. However, the end date of concomitant medications will be imputed as the last day of the month if only the day is missing, and as December 31st of the year if both the day and the month are missing. The above imputation is needed to properly identify treatment-emergent adverse events (TEAEs) and prior/concomitant medications.

Other missing data imputation.

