Missing OM data will be replaced using various algorithms, discussed in detail in Section 8.7.1 of this SAP.

No other missing data will be imputed.

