The effect of treatment on the primary efficacy endpoint will be examined within subject subgroups defined by region (US vs Europe), cisplatin regimen, HPV status and baseline disease characteristics (primary cancer diagnosis for 3 subcategories: oral cavity, oropharynx and all other). Descriptive summary statistics will be used for this purpose.

The following sensitivity analyses will be performed using alternative methods for the analysis of duration of severe OM in the ITT, mITT, and PP populations:

- Repeat the primary analysis using the worst adjacent imputation strategy for gap days, replacing the days without a value with the worst value between the closest previous and following values.
- Repeat the primary analysis but using imputation for missing data. For subjects with unresolved SOM, use the median value for subjects in the same treatment group with at least that duration. For subjects without severe OM but with incomplete follow-up (i.e., discontinued before the end of the active treatment period with no short-term follow-up OM assessments), use the median duration among patients in the same treatment arm who were free of severe OM for at least that length of follow-up.
- Calculate severe OM duration as the total number of days a subject has a grade 3 or 4 mucositis from the start of CRT until the end of the short-term follow-up phase, with last observation carried forward (LOCF) imputation (so, the OM grade at a day without assessment is considered to be the same as at the closest previous valid assessment).
- Same as the above, but using the worst adjacent imputation strategy for gap days (i.e. replacing the missing value with the worst value between the closest previous and following values).
- Repeat the primary analysis but using only the period from start of CRT to the actual last day of CRT to define duration of severe OM.

Listings of individual WHO OM grades and calculated primary endpoint values will be created.

The distribution of OM severity grades at each visit will also be displayed. These summary tables will present the number and percentage of patients per OM grade at each visit, by treatment group, for the ITT, mITT, and PP populations.

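### For subjects who leave early without severe OM, the one SAP 8.7.1 sensitivity analysis that changes their 0-day score uses a single own-arm median and is anti-conservative; the multiple imputation named in SAP 8.3 is never specified

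*SAP*

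**What the plan says.** SAP 8.7.1 sets the primary score: "Durations of 0 will be assigned to subjects who do not experience severe OM, even if the subject was not followed" to the planned end. SAP 8.3 gives the supporting analyses their task: "Sensitivity analyses will be performed to ensure that results of the primary efficacy endpoint are robust and not explained by missing or incomplete data".

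SAP 8.7.1 then lists five sensitivity analyses: worst-adjacent filling of gap days; a median imputation; total severe days with last observation carried forward (LOCF); total severe days with worst-adjacent filling; and a window limited to CRT. The median imputation has two halves, one for unresolved severe OM and one for subjects without severe OM who "discontinued before the end of the active treatment period with no short-term follow-up OM assessments". For the second group the rule is to "use the median duration among patients in the same treatment arm who were free of severe OM for at least that length of follow-up".

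On method, SAP 8.3 says "Where necessary, missing assessments of OM will be imputed using multiple imputation procedures", as does Protocol 10.9, and adds "Missing OM data will be replaced using various algorithms, discussed in detail in Section 8.7.1 of this SAP". SAP 8.7.1 contains no multiple imputation, and SAP 9 does not list it as dropped.

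For subjects never assessed, SAP 8.3 says "Worst-case assumptions will be applied to subjects who do not have OM assessments during the study period", but also "Rules for deriving efficacy endpoints will utilize imputation rules as specified in the efficacy analysis section". The efficacy section has no rule that names this group.

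**The concern.** A subject who leaves in week 2 without severe OM has mostly not yet reached the time at risk, so 0 days is a guess in the favourable direction. The sensitivity analyses exist to test that guess. For this group the test rests on one rule, which takes the arm difference seen among completers, copies it into the missing values and counts those values as data. The analysis can then look stronger than complete data would, and with no true effect it rejects too often in both directions. A reader of the study report could take such a result as evidence that missing data do not explain the primary finding. The multiple imputation that would carry the uncertainty is named, but nobody could program it from the SAP.

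**Working it through.** **The plan's own figure.** SAP 6: 80 per arm, difference 5 days, SD 10.8, two-sided 5%. Noncentrality = 5 / (10.8 × √(2/80)) = 5 / 1.708 = 2.93. Normal power = Φ(2.93 − 1.96) = 83.3%; the t-test gives 82.9%, against about 80% stated. The gap is conservative and does not bear on this point.

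**Which analyses move the score.** Take a leaver whose last grade is 2 or less.

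| Analysis in 8.7.1 | Score |
|---|---|
| 1. Worst-adjacent | No later value, last grade not severe: 0 |
| 2. Own-arm median | Changed |
| 3. LOCF | Non-severe grade carried forward: 0 |
| 4. Worst-adjacent, total days | As 1: 0 |
| 5. CRT-only window | Shorter window: 0 |

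**Simulation inputs.** From the documents: incidence 75%/50% and the 5% level (SAP 6), 1:1 allocation, three two-level factors (8 strata) and the modified-ridit CMH test (SAP 8.7.1), 100 per arm (200 enrolled, Protocol 4.1). Assumed: severe durations Normal(20, 7.45) days; onset Normal(28, 8) days; leaving at 5%, 10% or 20%, uniform over the stated days and independent of outcome; donors have complete follow-up. These match SAP 6: the difference is (0.75 − 0.50) × 20 = 5 days, and the SD at 75% is √(0.75 × (7.45² + 20²) − 15²) = √(341.6 − 225) = 10.8.

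**Mechanism.** At 75% incidence a quarter of donors score 0, so the median is the (0.50 − 0.25)/0.75 = one-third quantile of the severe durations: 20 − 0.43 × 7.45 = 16.8 days. At 50% incidence the median sits on the edge between 0 and the positive durations and jumps by chance. At 20% leaving on Days 1–14, leavers received on average 16.6 days (placebo) and 4.4 (AG013); the truth was 14.9 and 9.9. The arm difference becomes 0.8 × 5.0 + 0.2 × (16.6 − 4.4) = 6.4 days against a true 5.0.

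**Null error of the own-arm median, 75%/75%, equal leaving** (two-sided %, 3000 trials, simulation error 0.4–0.8 points):

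| Leaving | Days 1–14 | Days 1–28 | Days 1–49 |
|---|---|---|---|
| 5% | 6.6 | 7.5 | 6.3 |
| 10% | 11.4 | 10.0 | 7.7 |
| 20% | 26.2 | 20.9 | 11.0 |

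Over the same nine cells the 0-day rule gave 4.7–5.3% and a single median pooled over arms 4.4–5.5%. The inflation therefore needs both a fixed value and own-arm donors. Rejections split about evenly by direction (12.7% for AG013 and 13.5% for placebo in the 26.2% cell). With other assumptions (onset Normal(30, 8), Gamma durations with mean 15 and SD 10, leaving over Days 1–62) the error was 7.7%, 10.6% and 14.6% at 10%, 20% and 30% leaving, and 21.3% when 20% left on Days 1–29.

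**Power, leaving on Days 1–14** (complete data / 0-day rule / own-arm median, %). At 75%/50%: 87.4/84.9/90.3, 88.9/82.5/93.0 and 88.0/72.8/93.8 for 5%, 10% and 20% leaving. At an assumed 75%/60%: 46.2/42.3/50.7, 46.3/39.7/56.5 and 43.9/32.1/67.4.

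**Multiple imputation instead.** Hot-deck by days at risk with an approximate Bayesian bootstrap, M = 10, pooled on the rank statistic with variance W + (1 + 1/M)B. Own-arm donors gave null error of 4.8/4.7/4.5% (Days 1–28; 5/10/20% leaving), 5.0–5.7% under the alternative assumptions, and 4.2% and 5.5% in a smaller run (Days 1–14; 10% and 20%). Pooled or placebo donors gave 2.0–3.7%. Power at 75%/50%, Days 1–14, at 10% and 20% leaving: own-arm 83.1 and 79.8; pooled 76.4 and 65.6; placebo 76.8 and 66.1. In the same runs the own-arm median gave 91.1 and 95.5, the 0-day rule 81.4 and 75.1, and complete data 86.0 and 87.9.

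**Unequal leaving, no true effect** (false AG013 wins, %; nominal 2.5; 1000 trials, simulation error up to 1.6 points; rates assumed):

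| Placebo/AG013 leaving | Primary | Own-arm median | Both |
|---|---|---|---|
| 5%/25%, Days 1–14 | 46.7 | 9.0 | 8.9 |
| 5%/25%, Days 1–28 | 37.0 | 7.5 | 7.5 |
| 5%/25%, Days 1–49 | 18.8 | 5.9 | 5.9 |
| 5%/15%, Days 1–14 | 13.7 | 5.3 | 4.8 |

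In the first row the median removes 1 − 8.9/46.7 = 81% of false primary wins. Own-arm multiple imputation leaves about 2.5–4%; a separate 400-trial run of the first-row scenario gave 41% (primary), 9% (median) and 4% (own-arm imputation).

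**Never-assessed subjects.** Scoring one of 100 as 90 days rather than 0 moves an arm mean by 90/100 = 0.9 day. One such AG013 subject takes the difference from 5.1 to 4.2 days and power from 88.4% to 83.5%. One placebo subject takes them from 4.9 to 5.8 days and from 87.3% to 90.8%. One or two in each arm change power by 1 point or less.

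**The case against.** The best defence is that a sensitivity analysis licenses no claim alone; it qualifies a significant primary result. With equal leaving of 10% or 20%, the primary and the own-arm median both rejected in the same direction in only 2.9–5.3% of null trials. The 0-day rule is in real danger when AG013 subjects leave more often, and there the median overturns most false wins. This stands. A reader might infer that the check is worthless or that the trial's type I error is inflated; neither follows.

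A reader might also infer that nothing else protects against early leaving. The PP analysis does, in part. SAP 7.4 requires 50 Gy or an OM grade of at least 3; at 2.0–2.2 Gy a day, 50 Gy takes 25 to 23 fractions, about Day 33 to Day 31 at five a week. Leavers before then without severe OM drop out of PP, unless later radiotherapy is still recorded. Dropping them gave 2.1–2.9% false AG013 wins under unequal leaving on Days 1–14 and 1–28. But PP keeps a subject who reached grade 3 before 50 Gy and drops one who did not, so its selection depends on outcome, and it keeps later leavers at 0. Time to onset (SAP 8.7.2) censors these subjects, but it is a different endpoint.

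The size is uncertain too. The allowance from 200 to 160 subjects concerns IMP and radiation exposure, so it should not be read as a 20% leaving rate. Protocol 4.4 asks for end-of-phase procedures after discontinuation, the rule covers only leavers with no short-term follow-up assessment, and for late leavers the median can itself be 0.

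None of this justifies a fixed own-arm value where own-arm multiple imputation does the same job with nominal error.

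**Conclusion.** The point holds as a should-fix. For early leavers without severe OM, the only analysis in SAP 8.7.1 that tests the 0-day score is anti-conservative: null error of about 6–7.5%, 8–11% and 11–26% at 5%, 10% and 20% equal leaving, and apparent power above that of complete data. Under unequal leaving it is useful but leaves about 6–9% false AG013 wins at 5%/25%, more than own-arm multiple imputation. That multiple imputation is named but not specified follows from the text alone. The sizes rest on assumed leaving rates, timing, onset and duration; at 5% leaving the inflation is modest.

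The never-assessed group is a minor point. Reading SAP 8.7.1 literally, a reader might infer 0 days, or that the score is wholly undetermined. Protocol 10.5 assumes severe scores for such subjects in the incidence analysis, and SAP 9 withdraws that for incidence only, which suggests that the worst-case rule in SAP 8.3 still stands for duration. What is missing is the number of days and a statement of which rule governs. Such subjects should be few: randomization is at most 3 days before Day 1 (Protocol 7.2.2), an oral assessment is required on the day of withdrawal (Protocol 6.3.1), and mITT excludes them.

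**What to change.** SAP 8.1 allows updates until database lock. Before then:

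1. In the second sensitivity analysis of SAP 8.7.1, for leavers without severe OM, replace the single own-arm median with the multiple imputation named in SAP 8.3. Draw durations from same-arm subjects still free of severe OM at the same day at risk. State the number of imputations and how the stratified rank statistic is pooled. The 0-day primary score can stay.
2. Optionally add pooled or placebo donors as a more conservative stress test, and state the power loss. They should not be the main method: under random leaving they would often overturn a true effect.
3. State in 8.7.1 that the worst-case rule of 8.3, not the 0-day rule, governs ITT subjects with no post-baseline OM assessment, and give the number of days, for example severe OM to Day 91, the limit that 8.7.1 already uses.

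The cost is SAP wording and a little more programming, with no new data. The sensitivity result becomes less favourable: at 75%/50% with leaving on Days 1–14, about 83% and 80% power at 10% and 20% leaving, where the fixed median would show 91% and 95.5%.
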